To include the options of recall coordinated from within participating practices and centralised recall coordinated by the Primary Health Organisation (PHO).

To screen at least 3000 patients using their choice of one of the following tests:

- Vaginal hrHPV self-test performed at home or other suitable location
- Vaginal hrHPV self-test performed at the General Practice (GP) clinic (with or without nurse or kaiāwhina-led support)
- Clinician-taken cervical liquid-based cytology sample.

To implement NCSP-agreed care pathways for abnormal hrHPV screening results utilising cervical cytology, colposcopy and repeat screening.

To implement NCSP-agreed screening and care pathways for patients with previous abnormal cytology.

Objectives

Primary

To describe the impact of hrHPV testing (by demographics and screening history when numbers permit) in terms of:

- Proportion of patients screened by each method
- Proportion of patients who complete or do not complete each step of the appropriate screening pathway (including uptake of screening, cytology triage, and colposcopy assessment) and referral back to primary care
- Time to completion of the appropriate screening pathway
- Screening outcomes in patients with prior abnormalities in relation to transition guideline recommendations
- Number of colposcopy referrals, their indication, and outcomes.

To describe the disease burden detected in the study population, in terms of:

- HPV positivity rate by HPV 16/18 or other hrHPV, by demographics
- Incidence of CIN2+ in patients with HPV 16/18 by cytology result
- Incidence of CIN2+ in patients and with other hrHPV with abnormal cytology.

Secondary

To describe uptake of screening by mode of invitation:

- Centralised PHO or practice-based recall.

To describe resource utilisation (e.g. number of contacts, type of contact, engagement of other agencies, cost to patient) to achieve completion of the screening pathway:

- To achieve hrHPV screen
- In the event of an abnormal hrHPV screen, to achieve cervical cytology and/or colposcopy.

To report the rate of unsatisfactory hrHPV samples or documentation.

Equity

Compared to the general population, Māori and Pacific patients are less well served by the NCSP based in traditional primary care practices. The reason for introducing the HPV self-test is to reduce the incidence of cervical cancer and reduce inequities by providing a more sensitive test and reducing barriers to cervical screening.

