Patients with a previous high-grade abnormality or glandular abnormality, and who have not completed test of cure are recommended to undergo cytology at the time of hrHPV testing. If cytology or hrHPV testing is abnormal the patient should be referred to colposcopy. If a patient has had a prior low-grade abnormality (and no high grade) or has completed a test of cure they can be managed as per patients undergoing routine screening. When reporting the test, the laboratory will have access to the prior screening history. If a cervical cytology test (test of cure) is indicated but has not been taken, this will form part of the report.

Handling of specimens

Specimens will be delivered to the participating practice or central study location or the practice in person or by return courier envelope. The specimens will be logged and then sent on to the participating laboratory by courier or other suitable delivery mechanism. In some circumstances if a home test has been performed the specimen will be delivered directly to the laboratory. In this case consent forms will be collected by the laboratory and returned to the study centre. It is recommended that samples are sent to the lab within 48 hours of being taken. Results are to be reported within 5 working days of being received by lab.

Clinical responsibility for cervical tests

hrHPV tests organised by practice staff will be the responsibility of that practitioner (cervical screener).

hrHPV tests organised by the central recall system will be deferred to the designated lead in the practice. A method of coordination between the practice and the central recall will be determined. The centralised recall will be responsible for ensuring the designated practice is aware of the test and

the result. Patients with a positive result will require a face to face or a telehealth appointment to discuss the result.

Test Results

Test results will be reported according to normal locality and service-based protocols. The report will be issued to the clinician responsible for the test. A copy of the report will also be provided to the central study coordinator.

hrHPV results may be reported as follows

- Unsatisfactory test
- hrHPV Negative
- hrHPV Positive
- HPV 16 and or 18 and or HPV other(non-16 non 18 types) (extended genotyping may be reported if available)

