A recommendation for management will be included on the report according to the agreed management protocol after consideration of the patient's screening history and recorded presence or absence of symptoms.

Informing patients

Central recall (mail out)

If the test kit has been supplied directly from the central recall team, participants will be informed of their result by the central study nurse by a combination of letter, phone call, or text (preference will have been requested at the time of taking).

Practice taken or practice coordinated.

The patient will be informed of their result by the practice coordinating nurse or the patient's cervical screener by phone or text or letter as per normal practice.

Unsatisfactory

The test needs to be repeated at the patient's earliest convenience.

Negative hrHPV

A very low risk of cervical abnormality. Repeat screening test at normal recommended interval (*currently 3 years however will increase to 5 years with the new program*). However, if the patient has symptoms they should consult with their doctor. An exception to this is patients due to leave the NCSP screening programme. Please see Appendix 6.

Positive hrHPV (no reflex cytology)

The test has detected the presence of hrHPV. This indicates an increased likelihood of a cervical abnormality. Cervical cancer is very unlikely but further investigation is strongly recommended

HPV16/18

Participants positive for HPV 16 18 will be referred directly to colposcopy without delay. A cervical cytology test at this point is recommended but is not required.

HPV other

The patient will be advised to please make an appointment to undergo an examination and a cervical cytology test (smear) within 2 weeks by a cervical screener of their choice.

The making of appointments will be facilitated by the informant. The patient will be informed that there may be a charge for that appointment.

At this point a patient with a positive result may be referred to colposcopy if cytology triage is considered to be an unacceptable barrier, but the patient agrees to attend colposcopy.

Positive hrHPV with reflex cytology

If a cervical hrHPV sample has been taken and cytology triage has been performed, then this information and or the need to undergo colposcopy can be communicated with the patient face to face or by phone.

Referral to colposcopy

(See flow chart in Appendix 7)

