Data to be presented separately for participants negative for hrHPV, participants positive for HPV16 and/or 18, and participants positive for hrHPV other than 16 or 18.

The reason for no cytology report (prior to colposcopy) in participants positive for hrHPV and had a vaginal hrHPV test:

- Cytology not considered feasible by the GP
- Participant declined
- Participant unable to be contacted
- Other.

Data to be presented separately for participants positive for HPV16 and/or 18 and participants positive for hrHPV other than 16 or 18.

In participants that had a cytology test prior to colposcopy, the mean, median and range for the time between an hrHPV test result report being issued and a cytology sample being undertaken (prior to colposcopy).

Data to be presented separately for participants negative for hrHPV, participants positive for HPV16 and/or 18, and participants positive for hrHPV other than 16 or 18.

In participants that had a cytology test prior to colposcopy, the mean, median and range for the time from a cytology sample being undertaken to the results report being issued.

Data to be presented separately for participants negative for hrHPV, participants positive for HPV16 and/or 18, and participants positive for hrHPV other than 16 or 18.

In participants that had a cytology test prior to colposcopy, the number (and percentage) with a result of:

- Negative for dysplasia or malignancy
- ASC-US (atypical squamous cells of undetermined significance - excluding ASC-US possible high grade)
- LSIL (low grade squamous intraepithelial lesion)
- ASC-H (atypical cells of undetermined significance, possible high grade)
- HSIL (high grade squamous intraepithelial lesion)
- Cancer (invasive squamous carcinoma of the cervix)
- Adenocarcinoma
- Cancer other
- AGC/AIS (atypical glandular cells / adenocarcinoma-in-situ)
- Unsatisfactory sample

Data to be presented separately for participants negative for hrHPV, participants positive for HPV16 and/or 18, and participants positive for hrHPV other than 16 or 18.

In participants that had a cytology test prior to colposcopy, the mean, median and range for the time from their cytology sample being undertaken to being informed of the result.

Data to be presented separately for participants negative for hrHPV, participants positive for HPV16 and/or 18, and participants positive for hrHPV other than 16 or 18.

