The Ministry of Health reported NZ average is one full-time equivalent general practitioner (GP) per 1,650 patients and the average practice size is 3 full-time equivalent GPs. Thus, the average GP practice has 4950 patients on their books. Approximately, 32% of the NZ total population is female and between 25 and 65 years old.¹¹ Adding patients between 65 and 69 years and excluding patients who have had a hysterectomy, the average GP practice will have approximately 1600 patients who are eligible for 3-yearly cervical screening and thus, approximately 533 patients due for screening in any one year, and 266 patients due for screening per practice over the 6 month recruitment period. Assuming, 25% of patients do not wish to participate in the study, it would be possible to recruit 200

patients per practice over 6 months. We aim to include 15 general practices as recruitment sites. Thus, that would allow us to recruit 3000 patients over 6 months.

The acceptability and uptake of self-testing varies markedly in different studies depending on country, method of invitation, and demographics of the patients involved.^{8,12} Irrespective, the majority of hrHPV self-sample studies and surveys involve un- or under-screened patients,^{8,12-14} and the uptake in patients who usually participate in screening may differ. However, based on these previous studies, we estimate that 60-70% of patients may opt for self-sampling, thus we estimate that we will recruit 1800-2100 patients to the hrHPV self-sampling group and 900-1200 patients to the clinician-taken hrHPV test group. Based on previous studies,⁴ we estimate that 12% of hrHPV self-sampled tests will be hrHPV positive and an estimated 216-252 patients will need to return to their GP practice so that a follow-up cervical cytology sample can be taken. As this is a key safety concern, the number of patients in the hrHPV self-sample group who do not return for a clinician-taken cervical cytology sample within 3 months following a hrHPV positive result will be assessed. With a sample size of 216, there is 95% power to observe a failure to return rate of 2% or more.

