Serious adverse events will be reported to the study management team by filling out a Serious Adverse Event (SAE) report form and emailed within 7 days of the GP practice becoming aware of the event.

Serious Adverse Events include:

- Interval diagnosis of invasive cancer, CIN3, or AIS following a negative hrHPV test
- A screened person being given the wrong result
- A screened person being given the wrong advice following their screen (e.g., not referred to colposcopy or cytology when they should have been)
- A screened person not receiving the result of a positive test

Serious adverse events will be investigated as soon as possible by the study team and the relevant service provider to ensure similar errors do not occur and that there is no systemic case for this error.

The service provider will be responsible for the discussion of this adverse event with the person affected and their whanau and informing other agencies if appropriate. The study team will be responsible for informing the NCSP.

The following other adverse events will also be reported at completion of the study

- A person referred to colposcopy who does not attend within 3 months
- A person with other hrHPV who is recommended to have cervical cytology but who does not attend within 3 months

Site visits

Site visits will be performed either face to face or virtually by at least 1 member of the study management team, prior to commencing invitation to the study and within 3 months of commencing the study. Additional visits will be organised on request of the participating practice or if issues are perceived by the study management team.

The first visit is to ensure mechanisms of enrolment data management and clinical management of patients is understood by all members of the team. In addition, to ensure that systems are appropriate.

The second visit is to understand any issues of concern being encountered by the practice and to ensure ongoing participation of the practice team with screening and study protocols.

Further site visits may occur as required if areas of concern have been identified.

Audit

Prospectively-collected data will be collected in electronic case report forms (e-CRF) within 4 weeks of the event. 10% of data will be audited against source documents. If more than 10% of data is missing or incorrect, further in-depth audit will be undertaken.

Quality assurance

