As the NCSPR is not currently able to manage the results of hrHPV screening this information will be overseen by the study team. The study team will act in place of the NCSPR to provide reminders to the practices when patients are overdue further investigations or repeat testing and to ensure management recommendations are correct. Following colposcopy or on completion of the study when the NCSPR is able to manage these patients information they will be referred back to the NCSPR.

To ensure the clinical safety of participants. The redcap database will generate reminders to the general practice and to the study management team to ensure that critical parts of the patient care episode are completed. For example, informing patients of results, having a cervical cytology test and attending colposcopy within pre-determined time frames. While the general practice team will hold clinical responsibility for these actions the study management team will act as a safety net and prompt the clinicians involved. Thus, the database and the study management team are offering a greater degree of safety than the NCR, which at this point is unable to process hrHPV screening tests.

In addition, for all patients with an abnormal hrHPV test the recommendation recorded on the database will be cross checked against their result and cervical screening history to ensure this is consistent with guideline. Where this is not correct the inconsistency will be investigated by the study team and the provider.

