Appendix 6 Flowchart for management of hrHPV results either clinician taken or vaginal self-test

*Note if a vaginal self-test is taken and the result is positive a cervical cytology specimen is indicated to stratify risk, however in some circumstances it will not change so is

not required. (i.e. HPV16/18 positive) If a cervical test has been taken this will be performed on the same specimen by the laboratory. It is advised that this test is performed within 2 weeks.

**With the new five yearly screening interval, those coming in for their next screening test (after previous cytology screening) any time in the last five years before age 69, i.e. 65 – 69 years of age (inclusive), can exit the programme if their hrHPV test result is negative. This includes those with normal screening histories, with no screening history and those with previous abnormalities who have already been returned to regular interval (three yearly) screening. Exceptions are:

1. Participants who are still in active surveillance following previous abnormalities need to complete their follow-up. So if a test of cure is indicated and hasn't been successfully completed then they need a test of cure – one negative HPV test is not sufficient in this circumstance.
2. Immune deficient participants with a negative hrHPV test need to return in three years for a repeat hrHPV screen, if this falls before 69 years of age
3. Women who have had a recent hysterectomy will need a test of cure if there is high-grade histology in the hysterectomy specimen, which may or may not have been preceded by high-grade cytology.

[figure not shown]
Those who would normally exit the NCSP under the current NCSP exit requirements i.e. have had two normal screening cytology samples between ages 62 and 69 years of age, can exit at 69 years of age without HPV testing (providing not immune deficient or requiring further follow-up because of abnormal results).

***Urgency of referrals to Colposcopy are as follows;

- **Very Urgent** – Suspicion of Malignancy (10 working days)
- **Urgent** – High-grade cytology and/or HPV 16 or 18 positive (20 working days)
- **Semi-Urgent** – other high-risk HPV and low-grade/ASCUS cytology (3 months)
- Colposcopy can be referred as a clinical override e.g. hrHPV other and patient declining cytology triage.

ASCUS: Atypical Squamous Cells of Undetermined Significance hrHPV: high risk human papillomavirus NCSP: National Cervical Screening Programme

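### Missed test-of-cure cytology after a negative self-test is not directly measured: the non-completion outcome and the study team's history cross-check cover hrHPV-positive screens only

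*Protocol*

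**What the plan says.** **When cytology is recommended.** Under Patients with prior cervical abnormalities (Test of Cure), anyone with a previous high-grade or glandular abnormality and incomplete test of cure is recommended cytology together with the hrHPV test. This does not depend on the hrHPV result. The section foresees omissions: "If a cervical cytology test (test of cure) is indicated but has not been taken, this will form part of the report". Screening tests advises patients who need both tests to have a clinician-taken sample, so the group at issue is those who self-test all the same.

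**What is measured when cytology does not happen.**
- Outcome measures, Cytology: "The reason for no cytology report (prior to colposcopy) in participants positive for hrHPV and had a vaginal hrHPV test".
- Statistical Considerations: the number in the self-sample group "who do not return for a clinician-taken cervical cytology sample within 3 months following a hrHPV positive result will be assessed".
- Appendix 2, other adverse events: "A person with other hrHPV who is recommended to have cervical cytology but who does not attend within 3 months".
- Appendix 2, Quality assurance: "for all patients with an abnormal hrHPV test the recommendation recorded on the database will be cross checked" against the result and the screening history.
- Transfer of data and patient care to the NCSP: the one category for cytology declined or lost sits under an abnormal screen.

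**What the study sets out to describe.** The primary objectives include the proportion completing or not completing each step of the appropriate pathway, and "Screening outcomes in patients with prior abnormalities in relation to transition guideline recommendations".

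**What a negative result leads to.** The negative-result text under Test Results gives the routine interval and then one exception: "An exception to this is patients due to leave the NCSP screening programme". It refers to Appendix 6, where a note on leaving the programme at ages 65 to 69 says of outstanding test of cure that "one negative HPV test is not sufficient in this circumstance".

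**The concern.** The recommendation is triggered by history, while the measures of missed cytology are triggered by the hrHPV result. The two differ for a patient with test of cure outstanding who self-tests negative. A negative self-test treated as sufficient is an obvious way for self-testing to fail this group, and it is the case that the missed-cytology measures leave out.

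Two things are at stake. The first is description: the study exists to show where, and for whom, the pathway fails, and this step is part of two primary objectives. The second is safety: the study team stands in for the national register to ensure that recommendations are correct, but its stated check against screening history is confined to abnormal results.

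**Working it through.** This is a question of coverage, so the check is to list each relevant item with its population.

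| Item | Section | Population |
|---|---|---|
| Test-of-cure cytology recommended | Test of Cure | Incomplete test of cure, any hrHPV result |
| Reason for no cytology | Outcome measures | hrHPV positive, vaginal test |
| Non-return within 3 months | Statistical Considerations | hrHPV-positive self-testers |
| Missed-cytology adverse event | Appendix 2 | Other-hrHPV positive |
| Cross-check against history | Appendix 2 | Abnormal hrHPV test |
| Cytology declined or lost | Transfer of data | Abnormal screen |

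The first row includes hrHPV-negative patients. None of the other five does.

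**Can the count be recovered from other listed outcomes?**
1. Cytology invitations (0 to 3) are tabulated for participants recommended cytology, with hrHPV-negatives shown separately. This counts invitations, not completion. A patient wrongly given routine-interval advice may not be recorded as recommended cytology at all.
2. Cytology timing and results are shown for hrHPV-negatives, but only among those who had cytology.
3. Test of cure is a listed reason for cytology on the cervical hrHPV sample. For cytology performed after the hrHPV test, which is the self-tester's route, the only codes are a positive hrHPV result or another reason. Even completed test-of-cure cytology after a negative self-test is not identifiable there.
4. The screening-history split separates any prior treatment or abnormal screen from none. It pools outstanding test of cure with completed test of cure and with low-grade history, both of which the Test of Cure section manages as routine.
5. The handover list has a category for a normal screen with 12-month follow-up because of a previous abnormality. It does not record whether cytology is outstanding or was declined.

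No listed outcome, alone or combined, gives a direct count.

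**The plan's own figure.** Inputs, all from Statistical Considerations: 1800 to 2100 self-samplers and 12% hrHPV positive.
- Positives who need to return: 0.12 × 1800 = 216; 0.12 × 2100 = 252. This reproduces the protocol's 216 to 252.
- Self-samplers outside that assessment: 1800 − 216 = 1584; 2100 − 252 = 1848.

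The 1584 to 1848 are not the affected group. The affected number would be the self-testers with test of cure outstanding × the fraction of them hrHPV negative × the fraction without cytology. The protocol gives neither the first nor the last term, and its 12% positivity is not specific to this subgroup. The number cannot be computed.

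**The case against.** The strongest reply is that these patients are not invisible, and much of it stands.
- The laboratory sees the screening history and reports an indicated but untaken test-of-cure cytology at any hrHPV result. The study coordinator receives a copy.
- The recommendation on the report is made after considering screening history, so the negative-result text is not the only instruction.
- Wrong advice, including failure to send someone for cytology, is a serious adverse event for any screened person.
- Reminders about overdue investigations, with cytology named as an example, are not worded as applying to positives only.
- Invitations, test type, hrHPV result and any cytology result are all reported for hrHPV-negatives, and the handover list has a normal-screen category for previous abnormality.

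A reader might therefore be tempted to say that such a patient is missed by every check, or that a primary objective goes unmeasured. The protocol supports neither. Several safeguards apply at any result, and the prior-abnormality objective is partly served by the history split, the reasons for cytology and the results in hrHPV-negatives.

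Two further cautions stand. The Appendix 6 sentence is an exception to the exit rule for ages 65 to 69, so it is not by itself a general rule. The flowchart drawing was not available for this review, so the absence of a test-of-cure branch for negative results cannot be asserted.

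The safeguards still do not close the gap. The serious adverse event depends on the practice becoming aware of the error, and it does not cover a correctly advised patient who does not attend. The event for non-attendance at cytology is limited to other-hrHPV positives. A laboratory flag and a reminder are also not a reported count. The analysis could approximate non-completion from those recommended cytology and those who had it, but the limits at points 1 to 4 of the working would remain.

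**Conclusion.** The point holds in limited form. Non-completion of test-of-cure cytology after a negative self-test has no outcome, adverse event or handover category of its own, and it lies outside the study team's systematic cross-check. That part of the pathway-completion and prior-abnormality objectives is not directly measured, and protection for these patients is partial.

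The size is unknown. A reader might assume 2–5% of 3000 with incomplete test of cure, 20–50% of them self-testing and 80–93% of those negative. That gives 3000 × 0.02 × 0.20 × 0.80 = 9.6 up to 3000 × 0.05 × 0.50 × 0.93 = 69.75, or about 10 to 70. The first two rates have no source in the protocol, and the result counts people exposed to the gap, not missed cytology. It should not be used as an estimate.

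The study is descriptive and non-comparative, and no estimate or decision rule elsewhere in the plan fails because of this. It is an inexpensive improvement worth making, not a defect that must be fixed before the study can stand. The conclusion rests on the stated populations of the listed items; a separate analysis plan could add a tabulation but would not change the populations of the cross-check or the adverse event.

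**What to change.** 1. **Outcome.** Restate the no-cytology outcome for all participants with a vaginal test for whom cytology was indicated (hrHPV positive, test of cure incomplete, or symptoms): number with cytology, number without, and reason. Give hrHPV-negative test-of-cure patients their own row.
2. **Cross-check and adverse event.** Extend the Appendix 2 cross-check and the cytology non-attendance event to any participant whose laboratory report flags outstanding test-of-cure cytology.
3. **Handover.** Add a category for a negative hrHPV test with test-of-cure cytology outstanding.
4. **Text.** Reconcile the negative-result wording under Test Results with the Test of Cure section and the Appendix 6 note. Which clinical rule applies is for the sponsor and the screening programme to settle.

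The cost is protocol wording and a database query, since the laboratory flag and the screening history are already collected. The downside is a modest number of extra records to cross-check.
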